## **Aim of the study:**

1-To evaluate the efficacy of antibodies cocktail (casirivimab and imdevimab) compared to standard antiviral therapy in reducing 28-day mortality in hospitalized patients with moderate, severe or critical COVID19

2-To evaluate safety of antibodies cocktail (casirivimab and imdevimab) compared to standard antiviral therapy by monitoring of hypersensitivity and infusion related reactions or other significant adverse effects

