**Figure 2: Assignment of the included COVID cases at their groups.**

**Figure 3: Frequency of interventions in included patients**

## **Method:**

The type of this study is single blind non-RCT and is considered a Phase IV Clinical trial (post-marketing study) to report efficacy and safety of new medicine.

We use PubMed search tool to find clinical studies that performed to test efficacy and safety of developed immunotherapy in treatment of COVID-19 with about 4,000 results with focusing on antibodies developed as antiviral against COVID-19 obtaining only 70 results from which REGN-COV2, a Neutralizing Antibody Cocktail is selected with its only one clinical study up to now (REGN-COV2, a Neutralizing Antibody Cocktail, in Outpatients with Covid-19) which is published in New England Journal of Medicine on January 21, 2021.

Another resource used to obtain data is Fact Sheet for Health Care Providers-EUA OF casirivimab and imdevimab which provides clinical data about the use of this antibodies cocktail. Endnote citation software is used for citation of references.

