## **Statistical Analysis Plan (SAP):**

Intention-to-treat strategy will be used in this study. Intention-to-treat strategy will be used in this study. Statistical analysis will be achieved with SPSS, version 26.

Categorical variables will be presented as proportion and percent. Continuous variables will be presented as mean (standard deviation) for parametric data or as a median (25th-75th percentile) for non-parametric data.

Regarding baseline characteristics, Kruskal-Wallis or ANOVA test (depending on type of data and the continuous data distribution (normal or not)) will be used to compare these characteristics between the study groups. We will report the P-value for our statistical tests with level of statistical significance will be P-value  $\leq 0.05$ .

In case of existing differences in some baseline characteristics, logistic regression will be performed. This allows studying the effect of these variables on the primary outcomes of the study to exclude the effect of these confounding variables and to ensure the effect on the outcomes is due to interventions.

Regarding the outcomes, we will compare the 28-day all-cause mortality rate, result of PCR test at hospital discharge and incidence of infusion related or hypersensitivity reactions during and after the end of drug infusion (primary outcome) using the Kruskal-Wallis test with reporting the P-value.

While the secondary outcomes (hospital stay duration, icu stay duration and others) are compared using Kruskal-Wallis or ANOVA test depending on type of data and the distribution of data (normal or not)

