## **Sample Size:**

A total sample sizes of 246 patients would achieve at least 80 % power to detect a risk difference of 0.2 (20%) in the 28-day all-cause mortality (primary outcome) with a significance level ( $\alpha$ ) of 0.05 and 95% confidence level using the ANOVA or Kruskal-Wallis test of independent proportion in G\*Power software. To compensate for the estimated loss-to-follow-up and increase the study power, we will increase the sample size in both remdesivir and favipravir groups to be 106 patients compared to 53 patients in Antibodies cocktail Group As Antibodies cocktail product is available for only about 50 COVID-19 patients. In addition, the ratio (1:2:2) is the closest to reality according to number of patients who receive each drug.

The mortality data was estimated from the average mortality in August, September, and October 2021 at the Mansoura University Isolation Hospital among all hospitalized patients. Mortality rate is found to be about 360 cases in these 3 months (120 cases / month). The online system has been used to obtain mortality rate in these three months.

The current admission rate at the Mansoura University – Isolation Hospital is 250 cases per month on average; our needed sample is about 250 cases.

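### The primary safety comparison is a three-group P-value with no interval or margin; with 53 cocktail patients, a non-significant result could not support similar safety if reactions are uncommon

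*Combined protocol and SAP*

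**What the plan says.** Under Aim of the study, the second aim is "To evaluate safety of antibodies cocktail (casirivimab and imdevimab) compared to standard antiviral therapy by monitoring of hypersensitivity and infusion related reactions". Further adverse effects of importance are covered as well. The Method section gives the purpose of the trial as "to report efficacy and safety of new medicine". Under Outcomes, the third primary outcome is the percentage of patients with infusion-related or hypersensitivity reactions, together with reporting of serious and unexpected events.

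For reactions, the SAP compares "incidence of infusion related or hypersensitivity reactions during and after the end of drug infusion (primary outcome) using the Kruskal-Wallis test with reporting the P-value". The threshold comes from the sentence beginning "We will report the P-value for our statistical tests with level of statistical significance will be P-value", and is 0.05. The SAP also presents categorical variables as proportions and percentages. If baseline characteristics differ, it adds logistic regression on the primary outcomes. It names no confidence interval, risk difference, margin, tolerable rate or pairwise contrast for safety.

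The Sample Size section says that 246 patients "would achieve at least 80 % power to detect a risk difference of 0.2 (20%) in the 28-day all-cause mortality". It gives no expected reaction rate and no power for safety. The cocktail group is limited by supply: "Antibodies cocktail product is available for only about 50 COVID-19 patients". The final groups are 53, 106 and 106.

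**The concern.** A difference test takes no difference as its starting point and asks the data to overturn it. For efficacy that is conservative. For safety it is not: when events are few and the group is small, the test often stays non-significant although the new treatment causes more reactions.

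Here the group of interest is the smallest, its size was set by supply, and the outcome was not considered in the sizing. A P-value alone does not tell a reader how large an excess remains possible. What is at stake is how one of the two aims is reported, in hospitalised patients. By the protocol's own Introduction, the cocktail is not authorised for that group, and serious effects not previously reported can occur.

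**Working it through.** **Inputs.** Group sizes 53/106/106 come from Sample Size and Table 2, and match the 1:2:2 ratio under Interventions. The Population section states 2:1:1, which conflicts and must be reconciled separately. The test is a three-group Kruskal-Wallis at 0.05 (SAP). Reaction rates are not in the documents, so those below are assumptions shown over a range.

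**The plan's own figure.** One-way ANOVA with three equal groups, Cohen's f = 0.2 and alpha 0.05 has noncentrality 246 × 0.2² = 9.84 and power 0.804. So "A total sample sizes of 246 patients" is reproduced if 0.2 is read as f. It concerns mortality; there is no corresponding figure for safety.

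**Power of the safety test.** On a 0/1 outcome, the tie-corrected statistic is H = (N − 1)/N × Pearson chi-square, with N = 265, referred to chi-square on 2 df. Summing the three binomial probabilities over every outcome with H at or above the critical value gives exact power. The miss rate is 1 − power.

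| Cocktail / remdesivir / favipiravir (assumed) | Power | Missed |
|---|---|---|
| 1.5 / 0.5 / 0.5% | 0.089 | 91% |
| 3 / 1 / 1% | 0.170 | 83% |
| 6 / 2 / 2% | 0.285 | 71% |
| 9 / 3 / 3% | 0.385 | 61% |
| 15 / 5 / 5% | 0.590 | 41% |
| 30 / 10 / 10% | 0.890 | 11% |
| 6 / 2 / 0% | 0.581 | 42% |

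The last row allows for favipiravir being given orally or by tube, so that infusion reactions cannot occur in that group (hypersensitivity still can). Part of that power comes from the remdesivir-favipiravir gap. With 5/5/0%, where the cocktail has no excess over remdesivir, the test still rejects 60% of the time. For cocktail against remdesivir alone at 6% vs 2%, Fisher's exact test has power 0.243, so 76% are missed.

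**What a non-significant result can hide.** Take 4/53 (7.5%) against 2/106 and 2/106 (1.9% each). The pooled rate is 8/265 = 0.0302, Pearson chi-square is 4.640, H = 264/265 × 4.640 = 4.62, and P = 0.099. Against remdesivir the observed difference is 5.7 percentage points, with a Newcombe 95% interval of about −1 to +16 points. The planned test would report P = 0.10; the interval shows that a large excess is still possible.

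**What zero events would show.** With 0/53, the one-sided 95% upper bound is 1 − 0.05^(1/53) = 5.5%. The two-sided 95% upper limit is 1 − 0.025^(1/53) = 6.7%.

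**The case against.** **The plan never equates non-significance with safety.** A reader might infer that it does, because no other basis for a favourable conclusion is given. The documents do not support that reading: the aim is to evaluate by monitoring, the Method section says to report, and non-inferiority is not claimed. This stands. The risk is one of interpretation, which the plan does nothing to prevent.

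**The P-value is not all that is planned.** Percentages by group, reporting of serious and unexpected events, and conditional logistic regression are also there. This stands too, so it would be wrong to say that safety is judged only by a P-value. Nor is any test named for serious unexpected events; that part is already descriptive. But none of these comes with a stated precision, and the regression is conditional. At 6/2/2% it would have only about 53 × 0.06 + 212 × 0.02 = 7.4 events to work with.

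**The miss rate depends on an assumed rate.** It is near 7 in 10 only for comparator rates of about 2 to 2.5%. A reader might take that as a property of the design, or infer that a favourable result is likely whatever the true risk. Neither is right: a fivefold excess (10% vs 2%) is missed 36% of the time, 14% vs 2% about 13%, and 30% vs 10% about 11%.

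**An oral comparator changes the picture.** It raises the power of the overall test. But the 5/5/0% case shows that the extra rejections need not concern the cocktail, which is a reason to name the contrasts.

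**Conclusion.** The point holds in a limited form. The only prespecified unadjusted between-group comparison of the primary safety outcome is an overall P-value, without an interval, difference or margin, in a trial sized on mortality. If comparator reactions occur in 3% of patients or fewer, equally in both comparators, a tripling in the cocktail group is missed at least about 6 times in 10. A non-significant result could not then support a conclusion of similar safety. At 5% the miss rate is 41%, and at about 10% the test is adequate for a tripling. If favipiravir has no reactions, the figures are lower (42% at 6/2/0%), but the overall test then no longer isolates the cocktail.

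These figures rest on assumed rates and on full groups of 53/106/106. The gap in the reporting plan does not depend on them. It should be corrected, but it does not invalidate the trial.

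**What to change.** In the SAP, base aim 2 on estimation:

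- Report each group's reaction rate with an exact (Clopper-Pearson) 95% confidence interval.
- Report the cocktail-minus-remdesivir and cocktail-minus-favipiravir risk differences with 95% confidence intervals, by a method suited to small counts such as Newcombe's.
- State the largest excess that the data can rule out.
- State that a non-significant P-value will not be reported as evidence of safety or of no difference.
- Unless the investigators set a tolerable rate or margin before the data are seen, call aim 2 descriptive.

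In Sample Size, state that the 80% power refers to mortality only. Add that zero events in 53 cocktail patients would exclude only risks above about 5.5% (one-sided 95%) or 6.7% (two-sided 95%).

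The Kruskal-Wallis P-value can stay as a supplement. The cost is a few sentences, three exact intervals and two difference intervals, with no extra patients or data. The downside is a more modest safety claim.

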## **Outcomes:**

Parameters that will be assessed during hospitalization at day 0(baseline), day 3, 7, 14, 28 include:

- C-reactive protein (CRP)
- ferritin
- lactate dehydrogenase (LDH)
- D-dimer
- serum creatinine(S.Cr) and estimated creatinine clearance(CrCl)
- alanine aminotransferase (ALT), aspartate aminotransferase (AST), albumin, bilirubin

Clinical outcomes measured before & during intervention

1) Primary outcomes

- 1- 28-days mortality rate (efficacy).
- 2-PCR test results at end of hospital visit (efficacy).
- 3-precentage of patients who developed infusion related or hypersensitivity reactions during and after the end of drug infusion and reporting of any Serious and unexpected adverse events may occur that have not been previously reported with REGEN-COV use that may cause drug discontinuation (Safety).

2) Secondary outcomes

- 1-Need for invasive mechanical ventilation.
- 2- Invasive mechanical ventilation and oxygen support duration (days).
- 3- Time to clinical improvement (defined as 2 points reduction in the WHO disease ordinal progression scale(11&12) or discharge, whatever happens first)
- 4- ICU and hospitalization length of stay (days).
- 5- SOFA score(13) on day 0,3,7,14, and 28.
- 6- COVID19 WHO disease progression score(11&12) from day 0 to day 28.
- 7- Inflammatory markers including CRP, ferritin, LDH
- 8- liver and kidney functions

In addition to clinical outcomes measured before and during intervention, Vital signs, glasgow coma score (GCS),complete blood count (CBC), artierial blood gas (ABG) and prothrombin time (PT) is recorded at day0.

Patients' charactrestics(age,gender) and relevant medical and medication history and current COVID-19 treatment drugs will be recorded on admission

Duration of research will be about 6 months from Novmber 2021 to March 2022

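### The SAP specifies no between-group analysis of serious or other adverse events as such, although aim 2 sets out to compare them with standard antiviral therapy

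*Combined protocol and SAP*

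**What the plan says.** Three sections describe the safety outcome, each differently.

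- **Aim of the study, aim 2.** The purpose is comparative: "To evaluate safety of antibodies cocktail (casirivimab and imdevimab) compared to standard antiviral therapy". The means is "monitoring of hypersensitivity and infusion related reactions or other significant adverse effects".
- **Outcomes, primary outcome 3.** This has two parts. The first is a percentage: "patients who developed infusion related or hypersensitivity reactions during and after the end of drug infusion". The second is a reporting commitment: "reporting of any Serious and unexpected adverse events may occur that have not been previously reported with REGEN-COV use", limited further to events that may lead to discontinuation.
- **Statistical Analysis Plan.** Among the primary outcomes, the safety item compared is "incidence of infusion related or hypersensitivity reactions during and after the end of drug infusion (primary outcome) using the Kruskal-Wallis test". Mortality and PCR are the other two: "we will compare the 28-day all-cause mortality rate, result of PCR test at hospital discharge". A later sentence says that "the secondary outcomes (hospital stay duration, icu stay duration and others) are compared using Kruskal-Wallis or ANOVA test".

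Adverse events are not on the list of secondary outcomes. That list does include need for invasive mechanical ventilation, SOFA score, and liver and kidney functions.

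**The concern.** Aim 2 asks a comparative question about reactions and other significant adverse effects. The SAP answers it for reactions only. A patient with a non-fatal serious event that is not a reaction, such as a thrombotic or cardiac event, counts under aim 2 but is a non-event in the SAP's safety comparison. The trial could report no safety difference between groups while such events differed.

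Three features of this trial make that more than missing detail. The Method section gives efficacy and safety of a new medicine as the purpose. The Introduction says that serious effects not previously reported can occur and that the combination is not authorised for hospitalised patients, who are the population here; it lists reactions among the effects already confirmed. And favipiravir is given orally or by Ryle tube (Interventions), so group C cannot have an infusion reaction to its study drug, although it can have a hypersensitivity reaction. Reactions alone are a weak basis for a three-group safety conclusion.

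**Working it through.** **Step 1. Components side by side.**

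| Component | Aim 2 | Primary outcome 3 | SAP |
|---|---|---|---|
| Infusion-related or hypersensitivity reactions | compared | percentage | compared, primary |
| Serious and unexpected events | within other significant effects, compared | reported, if new to REGEN-COV | not named |
| Other significant adverse effects | compared | not named | not named |

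**Step 2. Does other text fill the gap?** The words about other secondary outcomes in the SAP reach only the secondary list, which has no adverse-event item. The general rule that categorical variables are shown as proportion and percent names no adverse-event variable and no time window. Ethical approval covers telling participants and the committee about unexpected risk, which is not an analysis.

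**Step 3. What serious harm is compared?** 28-day all-cause mortality is a primary outcome, labelled as efficacy in the outcome list. Ventilation, SOFA, and liver and kidney function are secondary outcomes. None is designated as safety, and none records an adverse event as such.

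**Step 4. What could an added comparison show?** The plan states no figure for safety to reproduce; its sample size rests on mortality. Inputs: group sizes 53, 106 and 106 (Sample Size; Table 2) and alpha 0.05. Event rates are assumptions. One anchor is the Sample Size section's 120 deaths and 250 admissions a month: 120/250 = 48%, roughly, since the periods may not coincide.

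For a yes/no outcome the Kruskal-Wallis statistic is H = ((N − 1)/N) × Pearson chi-square, here (264/265) × chi-square, referred to chi-square with 2 df (critical value 5.99). Power by simulation, with groups B and C equal:

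| Assumed rate, A v B and C | Power |
|---|---|
| 20% v 5% | about 85% |
| 25% v 10% | about 70% |
| 30% v 15% | about 60% |
| 10% v 5% | about 24% |
| 20% v 10% | about 41% |
| 63% v 48% | about 40% |
| 58% v 48% | about 20% |

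The last two rows apply if deaths count as serious events, so that the base is near 48%.

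**Step 5. Precision of an estimate.** The 95% half-width for the cocktail against one comparator is 1.96 × √(pA(1 − pA)/53 + pB(1 − pB)/106):

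- 20% v 5%: 1.96 × √(0.16/53 + 0.0475/106) = 11.5 points around a difference of 15.
- 10% v 5%: 1.96 × √(0.09/53 + 0.0475/106) = 9.1 points around a difference of 5.
- 63% v 48%: 1.96 × √(0.2331/53 + 0.2496/106) = 16.1 points around a difference of 15.

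If group A has no event of some type, the one-sided 95% upper limit is 1 − 0.05^(1/53) = 5.5%. An event with a true rate of 1% would be seen at least once in group A with probability 1 − 0.99^53 = 41%.

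**The case against.** A reader might infer that a difference in serious harm is never tested. The documents do not support that. Death, the most serious harm, is a primary comparison across all three groups, and ventilation, SOFA, and liver and kidney function are compared as secondary outcomes. Much serious harm in this population would show there.

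A reader might also infer that the SAP drops a comparative endpoint set in the outcome list. It does not: primary outcome 3 gives a percentage only for reactions and promises reporting, not comparison, of serious and unexpected events. Events defined as new to REGEN-COV cannot sensibly be tested against remdesivir or favipiravir. The conflict is therefore mainly with the comparative wording of aim 2, which is itself softened by speaking of monitoring.

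Third, high power for a serious-event test depends on a large excess over a low base rate. At 10% v 5%, or at a base near 48%, such a test would usually miss the difference.

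All three points stand and limit the claim. They do not close the gap: no analysis, not even a descriptive one, is specified for serious or other adverse events as such.

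**Conclusion.** The point holds in this limited form: the SAP's only safety comparison is reactions, so it does not cover what aim 2 says will be compared. Non-fatal serious events that are not reactions fall outside it. It should not be read as saying that serious harm goes untested.

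The documents fix no size, because they give no serious-event rate. Under the assumed rates, power for a test on serious events runs from about 20% to about 85%, so the case for change is completeness of the safety answer and not a promised significance result. The change should be made before data are seen; components chosen afterwards would leave the safety conclusion open to selective reporting.

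**What to change.** 1. Use one safety component list in aim 2, primary outcome 3 and the SAP.
2. Record serious adverse events in all three groups, not only events new to REGEN-COV.
3. Add to the SAP, in words such as: *For each group, the number and percentage of patients with at least one serious adverse event from first dose to day 28 will be given, with and without deaths, and likewise for other significant adverse events. Risk differences with 95% CIs will be given for the cocktail versus remdesivir and versus favipiravir, as estimates without a claim of significance. The conclusion on aim 2 will rest on these together with the reaction comparison.*
4. If power is quoted for serious events, show it as a range over stated assumptions.

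Showing the result with and without deaths keeps it from largely repeating the mortality outcome. The cost is SAP wording, one more table, and uniform recording of serious events in all groups. Sample size, treatment and visits do not change.

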### **Exclusion criteria**

Patient should not have any of the following to be included:

1-history of hypersensitivity or infusion related reactions after administration of monoclonal antibodies.

2-prior use of standard antiviral therapy (remedsvir or favipravir).

3-Current use of controversial antiviral therapy (hydroxychloroquine, ivermectin, nitazoxanide, oseltemavir, acyclovir, ribavirine, lopinavir/rotavirus, sofosbuvir, dectasevir, semipiravir, azithromycin).

4-patients expected to die within 48 hours.

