## **Interventions:**

Population included in this study will be assigned into 3 groups with 1:2:2 ratios to receive either antibodies cocktail or standard antiviral therapy (remdesvir, favipravir) as shown in table2 and figures 2 & 3.

Group A patients will receive REGN3048-3051(Antibodies cocktail (casirivimab and imdevimab) ) in low-dose regimen 1.2 gm (1200 mg of combined antibodies) diluted in 250 ml 0.9% sodium chloride solution as single I.V infusion over 30-60 minutes.

Group B patients will receive Remdesivir :

Day1 (loading dose): 200 mg (two 100mg vials) diluted in 500ml 0.9% sodium chloride solution infused I.V over 60 minutes

Day 2-5 or Day 2-10 (maintenance dose): 100 mg (one 100mg vial) in 250 ml 0.9% sodium chloride solution infused I.V over 30 minutes

Group C patients will receive Favipravir :

[figure not shown]
Day 1 (loading dose): 1600 mg (8 tablets) or 1800 mg (9 tablets) orally or in Ryle tube / 12 hours

Day 2-5 or day 2-10 (maintenance dose): 600 mg (3 tablets) or 800 mg (4 tablets) orally or in Ryle tube / 12 hours

[figure not shown]
Patients will be received standard of care by Physicians, Clinical pharmacist , Nurses and as guided by Egyptian COVID-19 treatment protocol.

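### Both aims compare the cocktail with standard antiviral therapy, but the primary outcomes are tested only by a three-arm Kruskal-Wallis P-value, with no cocktail contrast, effect estimate or confidence interval

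*Combined protocol and SAP*

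**What the plan says.** Aim of the study, item 1, is to evaluate the cocktail "compared to standard antiviral therapy in reducing 28-day mortality in hospitalized patients". Item 2 asks about its safety "compared to standard antiviral therapy by monitoring of hypersensitivity and infusion related reactions". Interventions keeps the same two-sided framing: patients are assigned "to receive either antibodies cocktail or standard antiviral therapy (remdesvir, favipravir"). Neither section says whether the comparator is groups B and C pooled or each taken separately.

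The SAP compares the three primary outcomes "during and after the end of drug infusion (primary outcome) using the Kruskal-Wallis test with reporting the P-value". It presents categorical variables as proportions and percentages. It adds a model on a condition: "In case of existing differences in some baseline characteristics, logistic regression will be performed". It names no cocktail contrast, follow-up comparison, between-group effect measure or confidence interval. A risk difference of 0.2 and a 95% confidence level appear only under Sample Size, as design inputs for an ANOVA or Kruskal-Wallis test.

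For safety, Outcomes counts "infusion related or hypersensitivity reactions during and after the end of drug infusion". Under Interventions, group C is treated "orally or in Ryle tube / 12 hours".

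**The concern.** A three-arm Kruskal-Wallis test rejects when any arm differs from any other. Rejection does not say that the cocktail differs from anything. If the plan is followed exactly, the P-value for Aim 1 can be driven wholly by remdesivir against favipiravir. The comparison that the aim asks for would then be chosen after the data are seen: pooled or separate, adjusted or not, and on which scale. No planned output gives the size of the cocktail effect or its uncertainty.

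The safety outcome has a further, secondary difficulty. An infusion-related reaction, and a window tied to the end of an infusion, cannot apply to patients treated by mouth or tube. A three-arm P-value therefore mixes route of administration with drug safety.

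**Working it through.** **Inputs.** Arm sizes are 53/106/106 (Table 2 and Sample Size), with no allowance for loss to follow-up because no rate is given. Two-sided alpha of 0.05 is assumed, since sidedness is not stated. Comparator mortality is also an assumption. Sample Size gives 120 deaths and 250 admissions a month, and 120/250 = 48%. However, the deaths are from August to October 2021 among all inpatients, the admissions are the current rate, and the trial excludes "patients expected to die within 48 hours". A range of 30% to 48% is used.

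**The plan's own figure.** Take a three-group ANOVA with 0.2 read as Cohen's f (an assumed reading). The noncentrality is N × f² = 246 × 0.04 = 9.84, and power is 0.804. At N = 243 power is 0.798, so 246 is reproduced. Two-proportion sizing at 40% against 20% also gives 3 × 82 = 246, but the documents state no such rates. The test named under Sample Size is in any case the three-arm one, not a cocktail contrast.

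**The test.** On 0/1 data, H = [(N-1)/N] × X², where X² = Σ nᵢ(pᵢ - p̄)² / [p̄(1 - p̄)], on 2 df, and P = exp(-H/2).

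**Hypothetical example.** Deaths are A 25/53 (47.2%), B 40/106 (37.7%) and C 61/106 (57.5%), so p̄ = 126/265 = 0.4755.
- The terms nᵢ(pᵢ - p̄)² are about 0.001 for A, 1.020 for B and 1.060 for C, in total 2.081.
- X² = 2.081/0.2494 = 8.34. H = 8.34 × 264/265 = 8.31. P = 0.016.

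Group A contributes almost nothing to this result. The contrasts, with pooled-variance z tests and Newcombe intervals, are:

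| Contrast | Difference, points (95% CI) | P |
|---|---|---|
| A vs B+C | -0.5 (-14.9 to 14.3) | 0.95 |
| A vs B | +9.4 (-6.5 to 25.2) | 0.25 |
| A vs C | -10.4 (-26.0 to 5.9) | 0.22 |
| B vs C | -19.8 (-32.3 to -6.4) | 0.004 |

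**How often this happens.** All 54 × 107 × 107 binomial outcomes were enumerated, with A at the average of B and C. The ranges cover average mortality of 30%, 40% and 48%.

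| B-C gap | Three-arm test significant | A vs pooled significant | Three-arm significant, but neither A vs pooled nor any Holm-adjusted A pair |
|---|---|---|---|
| 5 points | 9-10% | 5% | 4-5% |
| 10 points | 24-28% | 5% | 14-17% |
| 20 points | 75-83% | 5% | 44-47% |

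**Power for a 20-point difference, B and C equal (same enumeration).**

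| A vs comparators | Planned three-arm test | A vs pooled | One pair, unadjusted |
|---|---|---|---|
| 28% vs 48% | 66% | 77% | 68% |
| 20% vs 40% | 71% | 81% | 74% |
| 10% vs 30% | 83% | 91% | 85% |

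The pooled advantage depends on B and C being similar. At 28/43/53 the three-arm test has 78.5% and the pooled contrast 77%. At 48/48/28 the figures are 85% and 27%, while A vs C alone has 71%.

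**The case against.** The strongest reply is that the SAP does plan a logistic regression on the primary outcomes, with the stated purpose of attributing the effect to the interventions, and that group percentages will be shown. This stands in part. The stated purpose implies a treatment term, and baseline differences are plausible if allocation is not random. But the model runs only if baseline tests differ, and it names no reference arm, contrast, odds ratio or interval. Subtracting percentages gives neither an interval nor a pre-specified comparison.

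A second reply is that the 75-83% figure depends on the pooled reading. This stands: with A midway, the cocktail truly differs from each comparator by half the gap, so under separate comparisons the null is false. The 4-5%, 14-17% and 44-47% figures are the ones to use, because they require every cocktail contrast to be non-significant. They still depend on a B-C gap that the documents do not give.

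A third reply concerns safety. The absence of infusion reactions with an oral drug can be a genuine advantage, and Aim 2's comparator includes favipiravir. A reader might infer that group C should be dropped from the comparison. The documents do not support that. Nor are A and B matched on exposure, since A has one infusion and B has repeated infusions. What remains is that one three-arm P-value on the composite cannot separate these effects.

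A reader might also infer that the trial has 66% power rather than the stated 80%. That holds only near 48% comparator mortality; at 10% vs 30% the planned test has 83%.

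**Conclusion.** The concern holds as a mismatch between the aims and the primary analysis. The planned P-value can be significant without saying anything about the cocktail, and no cocktail effect or interval is pre-specified. How often this would happen depends on the B-C gap: about 4-5% of trials at 5 points, 14-17% at 10 and 44-47% at 20. These figures assume 53/106/106, average mortality of 30% to 48%, and cocktail mortality at the comparator average.

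Two stronger readings are not supported. Kruskal-Wallis is not invalid here: on binary data it is practically the Pearson chi-square test, and its type I error is close to 5%. A rejection caused by B against C is therefore a correct answer to a different question, not a false positive. Nor is the case mainly about power, since the direct contrast gains only when B and C are about equal. The size of the safety problem cannot be estimated, because the documents give no reaction rates. The change should be made; it does not call for a redesign.

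**What to change.** 1. **Aim of the study.** State whether standard antiviral therapy means B and C pooled, which the Interventions wording fits, or each separately.
2. **SAP, for 28-day mortality and PCR at discharge.** Make the cocktail contrast primary, with a risk difference and 95% CI. Keep Kruskal-Wallis as supporting. There are two options:
   - A vs B+C at two-sided 0.05, with A vs B and A vs C as supporting estimates that cannot claim success on their own. If either route could claim success, type I error would be about 6-6.5% per outcome.
   - A vs B and A vs C with Holm adjustment.
3. **Allocation.** Reconcile Population, which says patients are randomized, with Method, which calls the study a non-RCT. If allocation is not random, an unadjusted contrast does not answer Aim 1 either. Report the same contrast from a regression adjusted for pre-specified baseline covariates already collected, whatever the baseline tests show. Population's 2:1:1 ratio also needs reconciling with the 1:2:2 used elsewhere.
4. **Sample Size.** Restate power for the chosen contrast as a range over assumed comparator mortality, as in the power table above.
5. **Safety (secondary).** Report infusion-related and hypersensitivity reactions separately, with A vs B and A vs C differences and CIs. State how reactions are observed in group C.

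**Cost.** This means short edits to five sections (Aim, Population or Method, Outcomes, SAP, Sample Size), a reaction-recording item for group C in the electronic CRF, and no extra patients. Stated power may fall below 80% near 48% mortality, though the planned test is lower still there when B and C are equal (66% against 77% pooled). Pooling can mask a difference from one comparator (48/48/28: pooled 27%, A vs C 71%), so the pairwise estimates should always be shown. The composite safety outcome is split.
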